Any data or information shared for dissemination will be de-identified and the confidentiality of all participants will be strictly maintained. The only persons with access to protected health information (PHI) will include study investigators, research coordinators and those approved by the MUSC IRB. All data will be secured on MUSC servers, behind firewalls, with passwords protecting entry in these systems. All PHI will be obtained and managed in accordance with the HIPAA Privacy Rule (45 CFR Parts 160 and 164).

Increased scrutiny and remote monitoring using technology and a clinical pharmacist may lead to an increased awareness and documentation of medication side effects and adverse drug events. However, we expect these to be identified and managed very early in their course, before they can induce harm to the patient requiring further health care interventions. Early identification and resolution of medication errors, side effects and adverse drug events is the primary factor that we expect to be the mediator of reduced health care encounters and costs. To ensure this is occurring in a safe manner, the DSMP will include detailed monitoring of health care encounters and clinical outcomes, including acute rejection episodes and graft function. If there are signals that the intervention is actually inducing higher rates of these incidents, then the designated

safety officer, an experienced transplant physician, has the authority to stop enrollment and/or close the study (section E3.a). We fully expect these event rates to reduce in the intervention arm, as compared to the control arm. We do, however, have a comprehensive plan to address issues if this is, in fact, not the case.

Potential Benefits of the Proposed Research to the Subjects and Others

Patients in the intervention group may have reduced incidence and burdens associated with medication safety issues. This may potentially lead to reduced health care associated encounters, visits to the clinic and/or hospital and costs. Regardless, the completion of this study will produce data that will lead to a better understanding of the incidence, severity, root cause and potential outcomes associated with medication safety issues within kidney transplant recipients. This information can be utilized to design and test different intervention strategies to reduce these events, should the proposed intervention within this study fail to demonstrate meaningful results.

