The clinical transplant pharmacist will be alerted by the patient if there are medication changes made by outside providers, by way of making adjustments to the medication regimen in the mobile app. At this point, the patient will be contacted to evaluate the medication change and determine if the adjustment to the regimen is safe and effective. If the pharmacist deems this change to be of concern, they will work with the patient and transplant physician to alter the regimen in an appropriate manner. In addition, the pharmacist will be alerted if the patient has evidence of significant nonadherence ($\geq 20\%$ missed self-reported medication doses in the course of a week), if they have blood pressure or glucose values that fall into critical ranges or if there are alarming trends in their readings or symptom assessments from surveys. Upon receiving these alerts, the pharmacist will communicate with the patient, determine the root cause and coordinate care with other care providers as delineated at the bottom of Figure 4.

[figure not shown]
During televisit encounters, the transplant pharmacist will conduct a thorough medication review, evaluate for signs and symptoms suggestive of medication safety issues, screen for drug-drug and drug-disease interactions and provide recommendations to resolve identified issues to the patient and/or provider, when applicable. The clinical pharmacist will be alerted and evaluate each patient when making a transition of care (inpatient admission or discharge) to ensure accurate medication regimens are communicated to accepting teams and to the patient. The same ambulatory EPIC note template that is used by the clinical pharmacist during the usual care visits will be utilized for documentation during these telehealth encounters. EPIC is the inpatient and ambulatory EHR utilized within the study institution. The process used to resolve medication safety issues during distant monitoring is outlined in Figure 4. Once the clinical pharmacist identifies an issue, they will develop a management plan using the algorithm detailed in Figure 5, discuss the recommendations with the providers, agree on a plan, and implement the plan with direct patient follow-up. The algorithm in Figure 5 encompasses the major medication safety issues, including side effects, adherence, drug interactions and less than optimally controlled comorbid disease states.

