Home-based monitoring of blood pressures and glucoses, using the FORACare system, will also transfer into the application and the report dashboard.(42, 43) The app will also give providers the ability to create and send surveys to the patient. The survey will populate on the patients' home screen as an alert message. The alert message will not disappear until the survey has been filled out and submitted. Survey responses get recorded in the app and are incorporated into the report dashboard. As part of this study, patients in the intervention cohort will receive medication side effect surveys during gaps in transplant clinic visits. The survey was developed using the validated Memphis Medication Side Effect Survey, coupled with our formative research demonstrating which side effects are associated with the adverse drug events that are most commonly associated with hospital readmission.(44-46) Patients will complete this survey and this data will then flow into the report dashboard for review as aggregate and trend information. Thus, this mHealth system will allow both the patient and transplant pharmacist to track signs and symptoms of medication safety issues.

3.b Method for Assigning Subjects to Treatment Groups

Whether a patient is in the intervention group or the control will be by random selection using a random number generator in simple blocks of 8.

3.c Subject Compliance Monitoring

Monitoring for compliance with medications, clinic visits, blood pressure and glucose monitoring (if applicable) is a part of the intervention in the intervention cohort. If subjects are not complying with data monitoring in the intervention cohort, they will be contacted by the study pharmacist to encourage use of the smartphone and any relevant Bluetooth-enabled devices. If this does not resolve the noncompliance, the subject will be contacted by the study PI to discuss continued involvement in the study. These data will not be monitored real-time in the usual care cohort. Compliance with study data capture will be monitored by the study coordinators, who are completely independent of the pharmacists providing the interventions. They will gather data via direct subject interview and through review of the subject's electronic medical records.

3.d Blinding of Study Intervention

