To assess for adverse drug events, the research coordinator will review patient symptomology, vital signs and laboratory values. The research coordinator will be trained by the study pharmacists in identifying medication errors and adverse drug events, determining causality and grading the severity. To ensure objectivity and consistency in recording these events across both study cohorts, a number of safeguards will be instituted. First, the study investigators will utilize the same research coordinator to record all medication errors and adverse drug events. Second, this research coordinator will be completely independent of the telehealth intervention that is being performed and will be blinded to the patient’s randomized group. Third, only the medication errors and adverse drug events recorded by this research coordinator will be

used for data analysis. Finally, these patient assessments will be followed by an independent assessment by a clinical transplant pharmacist that is not associated with delivering the study intervention. This will ensure that event rates are not biased towards a higher capture rate in the intervention cohort, which will be receiving more intense scrutiny of their medication regimens by a clinical pharmacist.

E4 Study Outcome Measurements and Ascertainment

The primary outcome measure of this study will be the incidence and severity of medication errors and adverse drug events, which will be identified, categorized and compared between the intervention and control cohorts as detailed above and in the following sections. The exploratory outcome measures of this study are to compare the incidence and severity of acute rejections, infections, graft function, graft loss and death between research cohorts and measure the association between medication safety issues and these events. Demonstrating improvements in acute rejections, infections, graft loss or death within the intervention group will provide the data needed to design a larger, multicenter study (through dissemination efforts detailed at the end of this proposal). Additional data that will be gathered includes patient surveys to capture measures of sociodemographics, health literacy, depression, social support and trust. These are important variables that may modify or confound the impact of the intervention.

Study endpoint definitions and assessment plan:

The following will be used to define and capture data and events within this study:

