1. Medication errors will be defined as documentation that a patient is taking a medication in a manner that was not intended; synonymous with the definition developed by Overhage and utilized within our previous research.(11,14).
2. Adverse drug events will be defined according to the AHRQ Patient Safety Network, in which it describes an adverse drug event as “an adverse event (i.e., injury resulting from medical care) involving medication use”.(21) The severity of the adverse drug event will be defined according to a modified version of the CTCAE developed by the National Cancer Institute and utilized in our previous research. The CTCAE is a standardized classification system developed to assess the frequency and severity of adverse events. It was originally designed for cancer patients, but is now routinely utilized across multiple patient types in clinical research.(48, 49). In both the usual care and intervention arms, a highly trained clinical research coordinator will independently interview all participants at bimonthly intervals and review their medical records to capture and record all medication errors and adverse drug events, including timing, likely cause and severity of each event. To assess for medication errors, the research coordinator will review and compare the patient’s documented medication regimen in the electronic health record (the regimen intended to be taken) to the medication regimen actually being taken by the patient, which will be assessed using the patient’s medication bottles. To assess for adverse drug events, the research coordinator will review patient symptomology, vital signs and laboratory values. Prior to the study being opened for enrollment, the research coordinator will be extensively trained by the study pharmacists in identifying medication errors and adverse drug events, determining causality and grading the severity.

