3. Acute rejection will be defined as a renal allograft biopsy demonstrating at least grade 1A rejection by Banff '97 criteria or higher or treated borderline rejection.(50) All patients will be required to have biopsy confirmation of rejection episodes within 24 hours of onset of treatment for acute rejection, as per our protocol and usual. It is standard care that all kidney allograft biopsies performed for transplant recipients occur at the transplant center (study institution). Biopsies will be read by the local pathologist, as usual care. This pathologist will not be informed of participant participation in the study and will be blinded to cohort assignment. The study coordinator capturing clinical event data, different from the coordinator capturing medication error and adverse drug event data (to ensure blinding is maintained), will review the medical record at regular intervals to determine the incidence, timing, severity, treatment regimen and reversibility of each acute rejection episode for all study participants.

4. Infections will be defined as any diagnosed and treated infection, and will be sub-classified as bacterial, viral, or fungal etiologies. Flu-like illnesses and viral syndromes NOT requiring antimicrobial therapy will not be defined as infections for this study. Opportunistic infections will also be sub-classified for this study as viral, bacterial or fungal and defined as infections not seen in immunocompetent individuals; the most common opportunistic infections in kidney transplant recipients include CMV, BK, EBV and candidiasis.(51, 52) The study coordinator capturing clinical event data, different from the coordinator capturing medication error and adverse drug event data (to ensure independence is maintained), will review the medical record at regular intervals to determine the incidence, timing, severity, treatment regimen and cure timing of each infection episode for all study participants.

5. Graft function will be defined using the 4-variable MDRD equation to estimate GFR. This equation has been validated as an accurate reflection of true GFR within kidney transplant recipients.(53) Routine serum creatinine concentrations, which are measured as part of usual care, will be utilized to estimate GFR at these *approximate* time points: baseline, 3, 6 and 12 months post-enrollment.

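### The blinded event coordinator reads a medical record that holds pharmacist televisit notes for the intervention arm only, so primary-outcome capture can differ by arm and the blind can be broken

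*Combined protocol and SAP*

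**What the plan says.** Medication errors and adverse drug events (ADEs) together form the primary outcome (E4). One research coordinator, described in E3 3.e as blinded to assignment, records them in both arms, and only that coordinator's events enter the analysis. Under E4 item 2 the coordinator will "interview all participants at bimonthly intervals and review their medical records to capture and record all medication errors and adverse drug events". D3 3.c says of the study coordinators generally: "They will gather data via direct subject interview and through review of the subject's electronic medical records".

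D3 3.a describes what the intervention arm receives on top of usual care. A transplant pharmacist holds televisits, reviews the medications and looks for symptoms that point to a medication problem. On where this is written down: "The same ambulatory EPIC note template that is used by the clinical pharmacist during the usual care visits will be utilized for documentation during these" (the sentence ends by naming the televisits). The section then states what this system is: "EPIC is the inpatient and ambulatory EHR utilized within the study institution". The same section has the pharmacist enter app-reported medication changes into that record as self-reported medications.

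E3 3.e lists the safeguards: a single coordinator, independence from the intervention, use of that coordinator's events only, and a follow-up assessment by a pharmacist who does not deliver the intervention. It concludes: "This will ensure that event rates are not biased towards a higher capture rate in the intervention cohort". For rejection, E4 item 3 gives chart review to a coordinator "different from the coordinator capturing medication error and adverse drug event data (to ensure blinding is maintained), will review the medical record at regular intervals".

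**The concern.** The trial is open-label and at a single centre, so blinded outcome assessment is its main protection against assessment bias. That protection needs the assessor's sources to be the same in both arms and to be silent about the arm. The medical record is neither. It carries extra symptom-directed pharmacist notes for intervention patients, and those notes can identify the arm.

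Two separate biases follow. Extra notes give the coordinator more chances to find an event in the intervention arm, which would dilute a true benefit. Knowledge of the arm can sway judgements of cause and severity in either direction. The plan recognises the link between chart review and blinding in E4 item 3, where it separates the rejection coordinator from the event coordinator, but E4 item 2 sends the event coordinator into the same chart.

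**Working it through.** **Step 1. Is the record an outcome source?** Yes under E4 item 2, and D3 3.c agrees. The parallel description in E3 3.e does not mention a general record review. Even so, E3 3.e has the coordinator use the regimen documented in the electronic record as the comparator for medication errors, and review vital signs and laboratory values. The two sections need reconciling, and on either reading the coordinator opens the record.

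**Step 2. Does the record differ by arm?** Yes, through two entries that the text supports.
- Pharmacist televisit notes. D3 3.a, Table 2 schedules televisits twice monthly for high-risk patients (2 × 12 = 24 over a full year), monthly for moderate-risk patients (12), and none for low-risk patients. Triggered visits come on top. E2 confirms that this supplemental care belongs to the intervention group.
- App-reported medications entered as self-reported. These sit in the regimen used to judge medication errors, so both halves of the primary outcome are touched.

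**Step 3. Is either entry masked?** No section restricts what the coordinator or the adjudicator may see.

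**Step 4. Do the listed safeguards close the gap?**
- One coordinator gives consistent judgement but does not equalise what is there to be judged.
- Independence from the intervention does not stop the coordinator reading its notes.
- Counting only the coordinator's events does not help if the coordinator can record what the pharmacist charted.
- Adjudication works on events already recorded. It cannot supply events missed in controls.

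**Step 5. Illustration of size.** The documents give no capture rate, so the capture share below is assumed.

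Inputs from F1: control rate 87% for ADEs of CTCAE grade 3 or higher; 33% relative reduction, so the intervention rate is 0.87 × 0.67 = 0.5829; 52 per arm; two-sided 0.05.

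Power with unpooled standard error: Φ(|p1 − p2| / √[(p1(1 − p1) + p2(1 − p2))/n] − 1.96).

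Putting in the numbers: 0.2871 / √[(0.1131 + 0.2431)/52] = 0.2871 / 0.0828 = 3.47. Then Φ(3.47 − 1.96) = 93.4%, which reproduces F1's 94% to within a point. Using a pooled standard error under the null gives 91.9%.

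Let c be the share of intervention patients with no otherwise recorded event who gain one through record review, with controls unchanged. The recorded intervention rate is 0.5829 + c × 0.4171. The apparent reduction is 1 − that rate/0.87.

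| c | Recorded rate, intervention | Apparent reduction | Power, pooled null | Power, unpooled |
|---|---|---|---|---|
| 0 | 58.3% | 33% | 91.9% | 93.4% |
| 5% | 60.4% | 31% | 88.1% | 89.9% |
| 10% | 62.5% | 28% | 83.1% | 85.1% |
| 20% | 66.6% | 23% | 69.7% | 71.8% |
| 30% | 70.8% | 19% | 52.6% | 54.2% |

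If all 68 per arm contributed, the pooled figures would be 97.1% with no extra capture, 91.8% at 10%, 81.1% at 20% and 64.1% at 30%. The table models only the extra-detection bias. It does not model a shift in grading from knowledge of the arm.

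**The case against.** The case for the plan has several parts, and some of them stand.

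- **The note template is shared.** Usual-care pharmacist visits use it too, so a pharmacist note does not by itself reveal the arm, and low-risk intervention patients may have few extra notes. This stands. The record can reveal the arm but need not do so for every patient.
- **Blinded adjudication.** A pharmacist outside the intervention adjudicates, blinded, and this bears on bias in cause and severity. It stands in part. The plan does not say what the adjudicator is shown, and adjudication cannot equalise detection.
- **Blinding is qualified.** D3 3.d promises blinded collection only so far as practicable. But E3 3.e is unqualified, and filtering the encounters appears practicable.

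A reader might also infer three stronger things that the documents do not support.

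- **Home readings and side-effect surveys unblind the coordinator.** D3 3.a sends these to the app and its dashboard on a secure website. No section says that they are filed in the medical record.
- **The plan concedes biased capture.** D2 2.f says that monitoring "may lead to an increased awareness and documentation of medication side effects and adverse drug events". That is a possibility raised in a discussion of patient risk, and the same section expects event rates to fall in the intervention arm.
- **Extra capture would look like harm to the safety officer.** ADEs are reported to that officer by arm (E3 3.c). Under F1's assumed effect, though, even 30% extra capture leaves 70.8% in the intervention arm against 87% in control.

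**Conclusion.** The point holds as a structural weakness. The coordinator's source differs by arm, the arm-specific entries are not masked, and the listed safeguards do not equalise the source. Capture of both components of the primary outcome can differ by arm and the blind can be broken, so E3 3.e promises more than its procedures deliver.

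It would go too far to say that capture will differ, or by how much. Extra notes tend to raise intervention counts. Knowledge of the arm can move grading either way. The net direction is therefore unknown. The fall in ADE power at 52 per arm, from about 92-93% to 83-85% at 10% extra capture and 53-54% at 30%, rests on an assumed capture share, no extra capture in controls and F1's own rates. It shows sensitivity and is not an estimate. Because size and direction are unknown, this is a should-fix.

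**What to change.** 1. Reconcile E3 3.e with E4 item 2 so that both give one list of sources for ADEs and medication errors.
2. State in both places that the coordinator and the adjudicating pharmacist work from a record view or extract that omits the intervention pharmacist's telehealth encounters, app and dashboard data, and the source label on app-reported medications. The filter should target the pharmacist encounters, because E2 schedules four tele-assessments in both arms.
3. Keep every source that both arms share: the bimonthly interview; the medication regimen in the electronic record as the error comparator; clinic, emergency department and hospital records; and vital signs and laboratory values, including those from the month 6 and month 12 visits.
4. Report ADEs found by interview alone as a sensitivity analysis.

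The cost is protocol wording and an encounter filter on the extract. The downside is small: an ADE documented only in a televisit note, and found nowhere else, is not counted.

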Patients randomized to the intervention cohort will be provided the same usual care as the control cohort. In addition, this cohort of participants will receive clinical pharmacist-led supplemental medication therapy monitoring and management, utilizing a smartphone-enabled mHealth application, integrated with televisits and home-based monitoring of blood pressures and glucoses (when applicable). Subjects in this cohort will be provided with a mobile device/data plan if they are not current owners of an iPhone. All will also be provided with a Bluetooth-enabled, automated, cuff-style bicep home blood pressure monitor and a Bluetooth-enabled digital home blood glucose monitor. On the mobile device, a HIPPA compliant app developed by our collaborative group will be installed that displays the patient's medication list and alerts them when it is time to take each medication, requiring them to indicate if the medication was taken for adherence tracking. Through the app, medication regimen-specific symptom surveys will be pushed to patients that ask the frequency and severity of common side effects of their medications. The intervention will include a clinical transplant pharmacist telemonitoring patient medication adherence and blood pressure/glucose readings (if applicable) weekly and scheduling telehealth visits with patients, as outlined in Table 2.

[figure not shown]
Table 2 – Televisit schedule based on patient risk and events

Risk Level	Definition	Scheduled Televisits	Triggered Televisits
High	
Meets 2 or more of the following High-Risk Criteria
 
 • <80% adherence to medications • Missed clinic visits • Blood pressure outside of 20% of goal • <80% of blood sugars within goal range • Moderate to severe side effects 	Twice Monthly	
 • Patient reported medication change or initiation • New severe medication side effect • Critical home values of blood pressures or glucoses • Any transition in care
Moderate	
 • Meets 1 of the High-Risk Criteria 	Monthly	
Low	
 • Does not meet any of the High-Risk Criteria 	None Necessary	

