This is an open-label study, so subjects and the research team will be aware of the study assignment. Due to the nature of the intervention, blinding of the subject and research staff is unable to be performed. In order to minimize bias, data for outcomes will be collected by blinded study personnel, as much as feasibly possible.

E Study Procedures

E1 Screening for Eligibility

Adult (≥ 18 years old at the time of transplant) solitary kidney transplant recipients 6 to 36 months post-transplant that meet study eligibility will be approached by research personnel for consideration for participation at the time of a usual care clinic visit or healthcare encounter with the transplant team.

E2 Schedule of Measurements

All patients in both arms of the study will continue to receive usual post-transplant care. The supplemental care that is provided to the intervention group will all be via remote monitoring and televisits, also detailed in section above. In addition, there will be two study specific clinic visits and four televisits that occur in all patients (both control and intervention arms), as detailed in the table below. The Baseline visit will not be counted as a study visit, as this will be the usual care visit patients are identified, screened, consented and randomized at. The table below outlines these visits and what will be assessed during the visits.

Assessment	Base-line	Month 2	Month 4	Month 6	Month 8	Month 10	Month 12
Obtain informed consent, collect baseline patient and transplant information	X						
Assessment for medication errors				X			X
Tele assessment for medication errors		X	X		X	X	
Assessment for adverse drug events				X			X
Tele assessment for adverse drug events		X	X		X	X	
Assessment for health care encounters				X			X
Tele assessment for adverse health care encounters		X	X		X	X	
Chart review assessment for acute rejection(s)	X	X	X	X	X	X	X
Chart review assessment for infection(s)	X	X	X	X	X	X	X
Chart review assessment for graft function, graft loss and death	X	X	X	X	X	X	X

E3 Safety and Adverse Events

3.a Safety and Compliance Monitoring

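### Blood pressure and glucose ADEs can draw on home meters issued to one arm only, and the ADE safeguards do not say which readings count

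*Combined protocol and SAP*

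**What the plan says.** E4 makes the incidence and severity of medication errors and ADEs the primary outcome. Item 2 has one coordinator "independently interview all participants at bimonthly intervals and review their medical records to capture and record all medication errors and adverse drug events". On ADEs, it says: "To assess for adverse drug events, the research coordinator will review patient symptomology, vital signs and laboratory values". E3 3.e gives the same method.

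E2 sets the schedule: "there will be two study specific clinic visits and four televisits that occur in all patients". The clinic visits are at months 6 and 12, and the televisits at months 2, 4, 8 and 10. E2 also states: "All patients in both arms of the study will continue to receive usual post-transplant care".

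D3 3.a, on the intervention cohort, states: "All will also be provided with a Bluetooth-enabled, automated, cuff-style bicep home blood pressure monitor and a Bluetooth-enabled digital home blood glucose monitor". The readings pass to the app and to the pharmacist's dashboard. Pharmacist televisits are written up in the electronic health record, on the note template used for usual-care pharmacist visits. D3 3.c covers compliance with medications, clinic visits, and blood pressure and glucose monitoring. It says of controls: "These data will not be monitored real-time in the usual care cohort".

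E3 3.e lists four safeguards: a single coordinator, independent of the intervention and blinded to arm; analysis of that coordinator's events only; and a further assessment by a pharmacist who does not deliver the intervention. It concludes that these keep event rates from being biased towards higher capture in the intervention arm.

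**The concern.** The four safeguards govern who assesses and whose record counts. None governs which readings may be used as evidence. A fully blinded coordinator who has months of home readings for one patient, and only clinic readings for another, can find more blood pressure and glucose events in the first.

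The protocol sees the general risk. D2 2.f accepts that remote monitoring may lead to more ADEs being noticed and documented, and E3 3.e relies on the safeguards to remove the effect. With this route open, a null or adverse ADE result could not be told apart from better detection in the intervention arm.

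**Working it through.** **Routes by which a home reading can reach the coordinator**

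1. Interview. Every patient is interviewed every two months. Nothing tells the coordinator to disregard home values that a patient reports.
2. Record review. The coordinator reviews medical records (E4 item 2), and pharmacist televisits are documented there (D3 3.a). The documents do not say whether those notes contain home values, so this route is possible but not stated.
3. Dashboard. No access for the outcome coordinator is described.

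**What each arm has**

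- Both arms: the same six assessments, usual-care encounters and laboratory results.
- Intervention arm only: trial-issued meters, with weekly review of the readings by a pharmacist.
- Controls: possibly their own meters. Inability to measure one's own blood pressure, or glucose if diabetic, is an exclusion in both arms (D2 2.b).

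**Reproducing the F1 figure**

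F1 gives a control rate of 87% for grade 3 or higher ADEs, a 33% reduction, 52 per arm, two-sided α = 0.05 and 94% power. The intervention rate is 0.87 × 0.67 = 0.583, or 0.58 if the reduction is one third.

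With p̄ the mean of the two rates, SE₀ = √(2p̄(1−p̄)/n) and SE₁ = √([p₁(1−p₁)+p₂(1−p₂)]/n):

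- Pooled form, power = Φ[(d − 1.96·SE₀)/SE₁]. At p₂ = 0.583, (0.287 − 1.96 × 0.0874)/0.0828 = 1.397, giving 91.9%. At p₂ = 0.58 it gives 92.4%.
- Unpooled form, power = Φ[d/SE₁ − 1.96]. At p₂ = 0.58, 0.29/0.0828 − 1.96 = 1.54, giving 93.8%.

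The plan's 94% is therefore reproduced. The pooled form is used below.

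**Illustration: added detection in the intervention arm**

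Suppose home readings add an ADE in a fraction f of intervention patients who would otherwise be event-free. The observed rate becomes 0.583 + f × 0.417. The values of f are assumptions.

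| f | Observed rate | d | z | Power |
|---|---|---|---|---|
| 0 | 58.3% | 0.287 | 1.397 | 92% |
| 10% | 62.5% | 0.245 | 0.957 | 83% |
| 20% | 66.6% | 0.204 | 0.515 | 70% |
| 30% | 70.8% | 0.162 | 0.065 | 53% |

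**Illustration: no true effect**

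Suppose both arms truly have 87%, intervention events are fully captured, and control events are captured at an assumed 95%, 90% or 80%. Observed control rates are 82.7%, 78.3% and 69.6%. The same formula gives about a 9%, 21% or 58% chance of a significant result against the intervention.

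**Visit mode alone**

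If capture is equally incomplete in both arms, at an assumed 90% or 80%, observed rates are 78.3% v 52.5% or 69.6% v 46.6%, and power is 80% or 66%. Equal true rates remain equal when observed, so visit mode by itself costs power but creates no difference between arms.

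**The case against.** The strongest reply is that controls are not short of vital signs. The coordinator reviews them and need not measure them, and record review is part of the method. F1 expects a mean of 18.4 encounters per control patient per year, which E4 item 7 defines as face-to-face: 18.4/6 ≈ 3.1 per two-month interval. This stands. A reader might infer from the four televisits that controls have no reading for eight months of the twelve; the documents do not support that. Nor does the D3 3.c sentence on real-time monitoring mean that control readings do not exist.

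It can also be said that no text has the coordinator using home readings, that D2 2.f requires the same frequency and methodology in both arms, that E3 3.e adds blinded adjudication, and that G2 promises detailed algorithms that may settle admissible sources. This makes the bias a risk and not an established fact. It does not close the route, because none of these provisions, as written, limits the evidence.

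Finally, the likely direction is conservative: it threatens power more than it threatens a false claim of benefit. That also stands. However, a spurious excess of ADEs in the intervention arm would still mislead, both in the primary comparison and in the safety reports, which tabulate ADEs by arm (E3 3.c).

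**Conclusion.** The gap is real and worth closing, with medium confidence. The plan lets serial home readings reach the ADE assessment from trial-issued meters in one arm only, and its safeguards do not address this. Any bias probably raises the intervention ADE rate.

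Two stronger readings are not supported. One is that the televisit schedule itself biases the comparison; it is identical in both arms. The other is that the trial stands to lose a known amount of power. The 83%, 70% and 53% rest wholly on the assumed 10%, 20% and 30%. They also use a grade 3 or higher rate, while the modified CTCAE is not in the text available, so which blood pressure or glucose values reach that grade cannot be checked. The primary outcome in E4 is not limited to grade 3 or higher, so lower-grade findings could be affected too, by an amount the documents do not allow one to calculate.

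**What to change.** State in E3 3.e, E4 item 2 and the coordinator algorithm that, for the primary ADE comparison, blood pressure and glucose ADEs are identified and graded only from sources common to both arms: study clinic visits, usual-care encounters and usual-care laboratory results. State also that no home reading from any meter, in either arm, is used. The rule has to cover every meter, because asking a blinded coordinator to set aside only trial-issued readings would reveal the arm.

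Record the source of each ADE, and run a sensitivity analysis that adds back events supported only by home readings. An analysis limited to ADEs found at the two clinic visits would not serve: patients can report home readings there as well, and it discards other events without removing the source of the problem.

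The cost is a few sentences, one field on the case report form and one analysis. Some true ADEs seen only on home meters drop out of the primary comparison, though they return in the sensitivity analysis. Use of home readings in patient care is unchanged. One limit remains: a home reading may still prompt a usual-care visit at which the problem is then recorded, and this rule does not remove that.
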